10.3.3.3 Symptoms of Vulvar Vaginal Atrophy

At the Screening Visit, participants will rate the first 4 items in the list of VVA symptoms in [Table 10-3](#) as either not present (none), mild, moderate, or severe, and will indicate whether vaginal bleeding associated with vaginal activity is present or absent. They will then select 1 of the 5 symptoms as their most bothersome symptom. All 5 symptoms will be evaluated again during later study visits (see [Table 2-1](#)), and the change in severity from baseline will be determined. Changes from baseline in each participant's most bothersome symptom, as well as changes in dyspareunia (whether dyspareunia was the participant's most bothersome symptom or not), will be evaluated as study endpoints.

Symptoms to be evaluated are shown in [Table 10-3](#).

All participants will be required to engage in vaginal intercourse or other sexual activity (masturbation, etc.) at least 1 time between Days 49-56, and complete an assessment of VVA symptoms in their diary.

Table 10-3: Assessment of Most Bothersome Symptom

Symptom	Assessment
Vaginal dryness	None, mild, moderate, or severe
Vaginal and/or vulvar irritation/itching	None, mild, moderate, or severe
Dysuria	None, mild, moderate, or severe
Vaginal pain associated with sexual activity (dyspareunia)	None, mild, moderate, or severe
Vaginal bleeding associated with sexual activity	Presence versus absence

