2.2. Schedule of Events

Table 2-1: Schedule of Events

Day(s)	Screening	Administration Period														ET	FU		
		1-2 ^a				4 ^b	7 ^{a,b}	10 ^b	18 ^b	28 ^b	42 ^b	56-57 ^a							
Window	-	-				±1	±1	±1	±1	±1	±1	±1				-	±1		
Time from Admin. (hr.)		Pre-dose	0	4	10	24 ^c						Pre-dose	0	4	10	24 ^c			
Informed consent	X																		
Inclusion/Exclusion	X																		
Medical history	X																		
Concomitant medications	X	X					X	X	X	X	X	X					X	X	X
Physical exam ^d	X	X	X	X	X	X	X	X	X	X	X	X	X	X	X	X	X	X	X
Vaginal speculum exam ^e	X	X				X		X		X	X	X					X	X	X
Mammogram ^f	X																		
Cervical screening test ^g	X																		
Height and weight	X																		
Vital signs ^h	X	X		X	X	X		X		X	X	X		X	X	X	X	X	X
12-Lead ECG ⁱ	X	X		X				X		X	X		X		X		X	X	X
Serum biochemistry	X	X						X		X	X						X	X	X
Hematology	X	X						X		X	X						X	X	X
Urinalysis	X	X						X		X	X						X	X	X
Coagulation panel	X	X						X		X	X						X		X
TSH	X																		
FSH ^j	X																		
Drugs of abuse ^k	X																		
Viral serology ^l	X																		
Vaginal pH ^m	X	X							X	X	X						X	X	X
Vaginal cytology	X	X							X	X	X						X	X	X
Transvaginal ultrasound	X ⁿ																X	X	
Assessment of VVA symptoms ^o	X								X	X	X	X						X	X
Diary administration and review ^p	X	X					X	X	X	X	X	X						X	
Study drug administration ^q			X			X	X	X	X	X	X		X						
MENQOL		X															X	X	
Usability and Acceptability questionnaire						X					X						X	X	
PK blood samples ^r		X	0.5, 1, 2, 4, 5, 8, 12 (hr.)		X	X	X	X	X	X	X	X	0.5, 1, 2, 4, 5, 8, 12 (hr.)	X					X
AE ^s		X	X	X	X	X	X	X	X	X	X	X	X	X	X	X	X	X	X

Abbreviations: AE = adverse event; ECG = electrocardiogram; ET = early termination; FSH = follicle-stimulating hormone; FU = follow-up; HBsAg = hepatitis B surface antigen; HCV = hepatitis C virus; HIV = human immunodeficiency virus; hr. = hour; IP = investigational product; MENQOL = Menopause-specific Quality of Life; PK = pharmacokinetics; TSH = thyroid-stimulating hormone; VVA = vulvar vaginal atrophy

- a. Multiple non-PK assessments scheduled for the same time point should be performed on the same day as dosing. PK blood sample procedures should follow the defined window, if applicable.
- b. Samples for PK trough levels should be obtained prior to DARE-VVA1 insertion on Days 4, 7, 10, 18, 28, and 42. Administration of DARE-VVA1 will take place at site on the day of these visits, after collecting the trough PK sample.

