participants who have not had these tests in the timeframe indicated by the inclusion criteria. Participants will not be eligible if they have a medical history that suggests that they may be at risk of serious side effects of tamoxifen (e.g., thromboembolic disease, abnormal cervical screening results or history of endometrial pathology). Participants will also be excluded if they are receiving medications that could confound assessments (e.g., vaginal hormonal products, estrogen therapy, or use of SERMs or AIs within 6 months prior to screening) or have previously experienced an unsatisfactory outcome from a vaginal hormone therapy for VVA.

Preliminary efficacy will be assessed by vaginal cytology (for maturation index) and by vaginal pH, measured at baseline, every 2 weeks during treatment, following completion of treatment (Day 57), and at the follow-up visit conducted on Day 63. In addition, most bothersome symptom and dyspareunia will be evaluated during the treatment period and at follow-up. An exploratory assessment of quality of life will be conducted using the Menopause-specific Quality of Life (MENQOL) questionnaire, and participants will report on the usability and acceptability of DARE-VVA1 using a questionnaire.

In each treatment group, participants will have serial blood sampling for PK analysis, with venous samples drawn from an indwelling line. Dense sampling will be performed following the Day 1 and Day 56 administrations of DARE-VVA1; trough samples will be collected prior to dosing on Days 4, 7, 10, 18, 28, and 42, and a final sample will be collected at follow-up on Day 63. Samples will be analyzed using validated methods to determine plasma concentrations of tamoxifen and 3 metabolites: 4-hydroxytamoxifen, N-desmethyl-tamoxifen, and N-desmethyl-4-hydroxy-tamoxifen (endoxifen).

Safety will be assessed by evaluating AEs, vital sign measurements, clinical laboratory test results, 12-lead ECGs, and physical examination findings. In addition, vaginal speculum examinations will be performed, including an assessment of local irritation (in terms of erythema and edema). Women without a history of hysterectomy will undergo transvaginal ultrasounds at screening and at the end of treatment (Day 57).

Following the completion of treatment, participants will attend a follow-up visit on Day 63.

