8.2.1 Inclusion Criteria

Participants must meet all inclusion criteria to be eligible for enrollment into the study.

1. Women aged 40-75 (inclusive).
2. Postmenopausal women with a body mass index (BMI) between 18 and 38 kg/m², inclusive.
3. Postmenopausal, defined as:
 - a. For non-hysterectomized women, 12 months of spontaneous amenorrhea or 6 months of spontaneous amenorrhea with serum follicle-stimulating hormone (FSH) levels > 40 mIU/mL or 6 weeks postsurgical bilateral oophorectomy.
 - b. For hysterectomized women, serum follicle-stimulating hormone (FSH) levels > 40 mIU/mL or 6 weeks postsurgical bilateral oophorectomy
4. Have moderate to severe VVA as determined by self-assessment of the following symptoms: vaginal dryness, vaginal and/or vulvar irritation/itching, dysuria, vaginal pain with sexual activity (dyspareunia) (all self-assessed as none, mild, moderate, or severe), or vaginal bleeding associated with sexual activity (self-assessed as presence versus absence). To be eligible, at least 1 of the first 4 symptoms must be reported as moderate or severe, or vaginal bleeding associated with sexual activity must be present.
5. Women who currently have vaginal intercourse or other sexual activity (masturbation, etc.) at least once a month (with or without a partner), or who had intercourse or other sexual activity at least once a month in the past, but later decreased sexual activity due to excessive pain or vaginal dryness. Participants must be willing to engage in vaginal intercourse or other sexual activity (masturbation, etc.) at least 1 time between Days 49-56 of the clinical study.
6. Participants, upon pelvic examination with speculum examination, must have a normal-appearing vulva other than atrophic changes, and normal-appearing vagina (without erosions, ulcerations, scarring, or evidence of dermatoses) other than atrophic changes (loss of rugae, mucosal pallor, mucosal dryness, mucosal petechiae). Women without a cervix must have a normal-appearing vaginal cuff.

7. Women who have not undergone hysterectomy must have:
 - a. No prior history of endometrial ablation.
 - b. Endometrial thickness ≤ 4 mm on transvaginal ultrasound.
8. Women with a cervix must:
 - a. Have a normal appearing cervix other than atrophic changes (i.e., cervical stenosis and/or flushness with the vaginal wall)
 - b. Be current on all recommended screening and management requirements for cervical cancer.

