10.2. Study Periods and Visits

10.2.1 Screening

The participant must be screened within 21 days before enrollment in the study. Assessments to be conducted during screening are shown in the schedule of events (Table 2-1). No study-specific assessments should be conducted until the participant has provided written informed consent (see Section 14.4.1).

Participants who have not had mammograms and CSTs in the timeframe indicated by the inclusion criteria will undergo these assessments during screening.

Procedures for rescreening participants who initially fail to meet study entry criteria are described in Section 14.3.

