13. STATISTICS

13.1. Statistical Analysis

This section presents a summary of the planned statistical analyses. An SAP that describes the details of the analyses to be conducted will be written prior to database lock.

An analysis of covariance (ANCOVA) model will be used to assess treatment differences in change from baseline for vaginal pH, vaginal cytology, dyspareunia, and most bothersome symptom, using baseline score as a covariate. With no formal testing planned for this study, the *P* values will be informational.

Summary statistics will be provided for the variables described below. For continuous variables, these statistics will typically include the number of participants, mean, standard deviation (SD), median, minimum, and maximum. For categorical variables, these statistics will typically include the number and percentage of participants in each category. The denominator for percentage will be based on the number of participants appropriate for the purpose of analysis.

For all calculations of change from baseline, the last observation recorded before the first administration of the insert (DARE-VVA1 or placebo) will be considered as the baseline observation.

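### Symptom baseline is the screening rating that also decides entry, so within-arm change in the most bothersome symptom includes regression to the mean; a Day 1 rating would reduce it

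*Combined protocol and SAP*

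**What the plan says.** Section 10.3.3.3 describes the symptom rating: "At the Screening Visit, participants will rate the first 4 items in the list of VVA symptoms" (bleeding with sexual activity is recorded as present or absent). Directly afterwards, "They will then select 1 of the 5 symptoms as their most bothersome symptom". The next ratings are at later visits.

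In the schedule of events (Table 2-1), the row "Assessment of VVA symptoms" has a mark at Screening and none at Day 1 pre-dose. The rows for vaginal pH, vaginal cytology and MENQOL are all marked at Day 1 pre-dose. Section 7.1 agrees: "most bothersome symptom and dyspareunia will be evaluated during the treatment period and at follow-up", whereas pH and cytology are also measured at baseline. The diary symptom rating is tied to Days 49–56 and supplies no Day 1 value.

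The same self-rating is inclusion criterion 4 (Section 8.2.1): "To be eligible, at least 1 of the first 4 symptoms must be reported as moderate or severe", or bleeding with sexual activity must be present. On timing, Section 10.2.1 says: "The participant must be screened within 21 days before enrollment in the study".

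Section 13.1 defines baseline for every change score: "the last observation recorded before the first administration of the insert (DARE-VVA1 or placebo) will be considered as the baseline observation". For symptoms, that is the screening rating. Change to Day 56 in the most bothersome symptom and in dyspareunia are secondary endpoints (Sections 6.4 and 13.1.6.2). They are summarised by treatment group and analysed by ANCOVA with the baseline score as covariate and informational P values.

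**The concern.** One rating does three jobs: it admits the woman, it is the setting in which her endpoint symptom is chosen, and it is the value from which change is measured. A self-rating varies from day to day. Selecting women, and possibly symptoms, on a high value of a variable score and then subtracting that value produces apparent improvement without any treatment effect.

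What is at stake is the descriptive change by arm. Section 13.2 says the study is unpowered and is meant to guide later studies. With 8 women per arm, the change seen in an active arm could be carried into later planning, and part of it may be an artefact of where baseline was taken.

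**Working it through.** **1. Figures in the plan.** The protocol states no effect size, SD, power or reliability, so there is no figure of this kind to reproduce. The counts agree: 4 + 4 = 8 per arm and 5 × 8 = 40.

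**2. Is there any pre-dose rating other than screening?** Sections 7.1 and 10.3.3.3 name none. The middle columns of Table 2-1 may be displaced in a text copy, but the blank after the Screening mark agrees with both sections. The baseline is therefore the screening value.

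**3. Direction.** With reliability ρ, the expected change on retest of a selected score is roughly −(1 − ρ) × (selected mean − population mean). At ρ = 0.7 and population mean 1.5, the simulation below has a selected screening mean of 2.51, so −(1 − 0.7) × (2.51 − 1.5) = −0.30. The simulated value is larger (−0.43), because rounding to four grades lowers the reliability of the recorded score and the woman's other, lower ratings pull the retest value down further.

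**4. Size, simulated with no treatment effect.** Each of four symptoms is scored round(μ + √ρ·b + √(1 − ρ)·e), truncated to 0–3, where b is the woman's stable level and e is fresh error at each visit. A woman enters if any screening score is 2 or more. Assumed values, none from the protocol:
- ρ from 0.5 to 0.9
- μ from 1.0 to 2.0
- correlation of 0.3 between symptoms
- independent errors between visits

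Mean change from the screening baseline:

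| μ | ρ | Highest-rated symptom chosen | Choice independent of screening error | Dyspareunia |
|---|---|---|---|---|
| 1.0 | 0.5 | −0.76 | −0.18 | −0.09 |
| 1.0 | 0.7 | −0.52 | −0.15 | −0.06 |
| 1.0 | 0.9 | −0.26 | −0.09 | −0.03 |
| 1.5 | 0.5 | −0.63 | −0.07 | −0.04 |
| 1.5 | 0.7 | −0.43 | −0.06 | −0.03 |
| 1.5 | 0.9 | −0.22 | −0.04 | −0.01 |
| 2.0 | 0.5 | −0.51 | −0.02 | −0.01 |
| 2.0 | 0.7 | −0.36 | −0.02 | −0.01 |
| 2.0 | 0.9 | −0.18 | −0.01 | −0.01 |

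Dyspareunia is analysed whether or not it was the chosen symptom, so only the entry rule acts on it.

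At μ = 1.5, ρ = 0.7 and highest-rated choice, 44% of women improve by at least one grade from screening, against 24% from a separate Day 1 rating. A within-arm t-test at n = 8 (not planned, shown only for scale) is falsely positive in 34% of arms from screening and 5% from Day 1.

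**5. Comparison between arms.** In 4,000 simulated 8-versus-8 trials at the same setting, the mean difference is 0.00 with either baseline. The ANCOVA false-positive rate is 5.4% (screening) and 5.1% (Day 1). The simulation error is √(0.05 × 0.95 / 4,000) = 0.3 percentage points, so neither differs from 5% by more than chance.

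**6. Precision.** In a separate simulation under highest-rated choice, adding Day 1 as a second covariate lowers the residual SD from 0.850 to 0.795 (ρ = 0.6), 0.747 to 0.689 (ρ = 0.7) and 0.636 to 0.578 (ρ = 0.8). The variance reductions are 1 − (0.795/0.850)² = 13%, 1 − (0.689/0.747)² = 15% and 1 − (0.578/0.636)² = 17%. Across ρ of 0.5 to 0.9 and both choice rules the range is about 5% to 20%.

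**7. What a Day 1 baseline leaves.** With independent errors, the null change is 0.00. If screening and Day 1 errors correlate at 0.3, about −0.03 to −0.19 remains over the same grid under highest-rated choice. At μ = 1.5 and ρ = 0.7 this is −0.10, against −0.44 from screening; at a correlation of 0.6 it is −0.20. If Day 1 were also used to gate entry, −0.01 to −0.14 would remain even with independent errors.

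**The case against.** **The placebo comparison is protected.** A reader might infer that the screening baseline biases the estimated effect against placebo. The documents do not support that. Randomisation gives every arm the same expected shift, the plan specifies a baseline-adjusted ANCOVA, and placebo is summarised beside each dose. This objection stands in full and confines the point to within-arm change.

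**The size is not known.** A reader might take the larger figures as the expected bias. Section 10.3.3.3 does not require a woman to choose her highest-rated symptom, and she may choose bleeding, which is binary and is not in the simulation. If the choice does not depend on screening error, the shift is at most about −0.18. This stands, so both ranges have to be shown.

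**Dyspareunia is barely touched.** This stands: the shift is below 0.1 throughout.

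**A Day 1 rating may not remove the problem.** Inclusion criterion 5 admits women active about once a month, or who have cut back because of pain or dryness, and activity is required only on Days 49–56. Some women will have had no new episode between screening and Day 1, and would re-report the old one or have nothing to rate. This stands: the remedy reduces the artefact, and these items need their own rule.

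**The endpoints are secondary.** The primary objectives are safety and PK, and no primary efficacy analysis is planned. This limits the weight of the point. It does not make the descriptive change by arm easier to interpret.

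**Conclusion.** The point holds for within-arm change in the most bothersome symptom. The protocol makes the eligibility rating the baseline, and regression to the mean follows from that. With no treatment effect, the built-in change is about −0.18 to −0.76 points if the highest-rated symptom is chosen, and about −0.01 to −0.18 if the choice does not depend on screening error. Both ranges rest on assumed reliability of 0.5 to 0.9 and population means of 1.0 to 2.0. The direction follows from the design; the magnitude cannot be read from the documents.

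The randomised comparison is unbiased with either baseline, and a Day 1 rating would add only precision there. This is a cheap improvement to a preliminary-efficacy endpoint and not an error that undermines the trial.

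**What to change.** Add a mark for the symptom assessment at Day 1 pre-dose in Table 2-1 and amend Section 10.3.3.3, so that women repeat the five-item rating before dosing, when MENQOL is already completed. This belongs in the protocol, because an SAP written later cannot supply a rating that was never collected.

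- Use the Day 1 rating as baseline for change in the most bothersome symptom and dyspareunia. The existing rule in Section 13.1 then selects it without rewording.
- Keep the screening rating for eligibility and for choosing the symptom, and add it as a second ANCOVA covariate.
- State that Day 1 is not a second entry gate.
- For the two sexual-activity items, record whether there was activity since screening. If there was none, carry the screening value forward as baseline and flag it. For those values the artefact remains, so report how many there are per arm.

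The cost is one short self-rating at an existing visit and one residual degree of freedom (40 − 5 − 1 = 34 becomes 33 if one model is fitted to all five arms). Apparent within-arm improvement will be smaller, some women will rate below moderate on Day 1, and some sexual-activity items will have no new Day 1 value.

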10.3.3.4 Menopause Quality of Life

The MENQOL™ questionnaire will be given to participants before the first dose and on Day 57, in accordance with the schedule of events ([Table 2-1](#)). Developed in 1996, the MENQOL is a self-administered, 29-item questionnaire with 4 domains: vasomotor, physical, psychosocial and sexual. Participants record whether they have experienced the listed problems in the past month, and rate the severity on a Likert scale from 0 (Not at all bothered) to 6 (Extremely bothered).^{20,21}

10.3.3.5 Usability and Acceptability Questionnaire

A Usability and Acceptability questionnaire will be administered to all participants in accordance with the schedule of events ([Table 2-1](#)).

10.3.3.6 Participant Diaries

Throughout the 56-day administration period, participants will be asked to record their administration of DARE-VVA1 on a paper diary, including the time of placement. Deviations from the planned doses (missed dose or timing) will be recorded on the participant's eCRF.

In addition, participants will be required to engage in vaginal intercourse or other sexual activity (masturbation, etc.) at least 1 time between Days 49 to 56 (see Section 10.3.3.3). Participants will use their diaries to capture their assessment of VVA symptoms.

Study personnel will review diaries at each visit, and diaries will be collected as source documents. Information from participant diaries will be transcribed on the appropriate eCRF pages for documentation of participant compliance with the IP.

10.3.3.7 Pharmacodynamics

Pharmacodynamics will be assessed by correlating the dose administered to dose exposure of tamoxifen in plasma, and then by relating the exposures to local vaginal changes in cytology and pH as well as to the reported symptomatology over 56 days.

11. ADVERSE EVENTS

11.1. Definitions

11.1.1 Adverse Events

An AE is defined as any untoward medical occurrence in a patient or clinical investigation subject administered a pharmaceutical product and which does not necessarily have a causal relationship with this treatment. An AE can therefore be any unfavorable and unintended sign (including an abnormal laboratory finding, for example), symptom, or disease temporally associated with the use of a medicinal product, whether or not related to the medicinal product.

Pre-existing diseases or conditions will not be considered AEs unless there is an increase in the frequency or severity, or a change in the quality, of the disease or condition. (Worsening of a pre-existing condition is considered an AE.)

Events that occur in participants treated with control product, or during treatment-free periods of the study, are also considered AEs.

11.1.2 Adverse Drug Reaction

All noxious and unintended responses to a medicinal product related to any dose should be considered adverse drug reactions (ADRs).

The phrase “responses to a medicinal product” means that a causal relationship between a medicinal product and an AE is at least a reasonable possibility, i.e., the relationship cannot be ruled out. All AEs judged by either the reporting investigator or the sponsor as having a reasonable causal relationship to an IP qualify as ADRs.

All AEs for which the judgment of relationship to IP is “possibly related” or higher will be considered ADRs. If a relationship to IP is not provided, then the AE must be treated as if it were “possible.”

11.1.3 Unexpected Adverse Event/Adverse Drug Reaction

An expected AE or ADR is one for which the nature or severity is consistent with the applicable scientific information (e.g., IB for an unapproved IP or Product Information document or similar for an approved, marketed product).

An unexpected adverse event (UAE) or unexpected adverse drug reaction (UADR) is one for which the nature or severity is not consistent with the applicable product information (e.g., IB for an unapproved IP or package insert/summary of product characteristics for an approved product). For example, hepatic necrosis would be unexpected (greater severity) if the IB only listed elevated hepatic enzymes or hepatitis. Likewise, cerebral thromboembolism and cerebral vasculitis would be unexpected (greater specificity) if the IB only listed cerebral vascular accidents.

Furthermore, reports that add significant information on specificity or severity of a known, already documented adverse reaction also constitute unexpected events. Examples would be (a) acute renal failure as an expected adverse reaction with a subsequent new occurrence of interstitial nephritis (interstitial nephritis would be unexpected) and (b) hepatitis with a first occurrence of fulminant hepatitis (fulminant hepatitis would be unexpected).

